## 9.2 Populations for Analyses

For purposes of analysis, the following populations are defined:

Population	Description
Full analysis set (FAS) population	All subjects who received at least 1 dose of MT-3724 monotherapy treatment. This will be the primary population for the assessment of efficacy endpoints.
Modified full analysis set (mFAS) population	All subjects who have at least 1 post-baseline efficacy assessment; subjects without a post-baseline efficacy assessment will not be considered evaluable for the primary efficacy analysis. Subjects who discontinue due to disease progression or die, prior to disease assessment will be included.
PK analysis population	All subjects who received any amount of MT-3724 and for whom the on-treatment PK data are considered to be sufficient and interpretable.
Immunogenicity analysis population	All subjects who have received any amount of MT-3724 and have valid post-baseline immunogenicity assessment will be included in the analysis set for the immunogenicity analysis.
Pharmacodynamic analysis population	All subjects who have received any amount of MT-3724 and have at least 1 valid post-baseline pharmacodynamic assessment.
Safety analysis population	All subjects who received at least 1 dose of MT-3724 monotherapy treatment. For this study, this is equivalent to the FAS population.

## 9.3 Statistical Analyses

### 9.3.1 General Considerations

Starting with Amendment 9 of the study protocol MT-3724\_NHL\_001, the study will be a multi-center, single-agent, open-label study consisting of 2 parts: Part 3 will complete the Phase 1b portion of this to verify the safety, dose and dosing schedule. Part 4 is a Phase 2 design and will provide independent confirmation of the efficacy of MT-3724.

Each of the 2 parts (Parts 3 and 4) will include LTFU after the last dose of MT-3724 for up to 18 months from the last dose. Subjects who discontinue the study for disease progression will be followed only for OS. Subjects who discontinue the study for reasons other than disease progression will be followed for PFS, as reported by investigators and OS.

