#### **4.1.2      Part 4**

The goal of Part 4 is to provide sufficient evidence to test the null hypothesis that the true response rate with MT-3724  $\leq$  17% vs the alternative hypothesis that the true response rate with MT-3724  $\geq$  32% at the 1-sided alpha level of 0.025 with high statistical power. At least 88 evaluable subjects will be required to test the null hypothesis vs the alternative hypothesis in Part 4. If at least 23 of 88 subjects respond at the end of Part 4, then the null hypothesis is rejected in favor of the alternative hypothesis and the effectiveness of MT-3724 as monotherapy will have been proven. Under the stated null and alternative hypotheses, Part 4 carries 90.4% power at the 1-sided alpha level of < 0.025.

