# **7 SUBJECT WITHDRAWAL, REPLACEMENT AND STUDY DISCONTINUATION**

## **7.1 Subject Withdrawal**

Subjects must be withdrawn from the study at their own request or at the request of their legally acceptable representative. The subject has the right to withdraw from the study at any time for any reason, without the need to justify his/her withdrawal. The subject will not suffer any disadvantage because of the withdrawal.

Subjects must also be withdrawn if the  $\beta$ -HCG pregnancy test indicates that they are pregnant at any time from signing the consent until the EoT Visit.

The subject may be withdrawn from the study at the discretion of the investigator due to:

- Safety concerns
- Lack of clinical benefit (disease progression is not documented but the investigator determines that the subject requires alternative anticancer treatment)
- Non-compliance with study procedures to the extent that precludes the assessment of study objectives

All subjects who permanently discontinue study treatment for any reason should have an EoT Visit performed as described in the Schedule of Activities ([Section 1.3](#)).

The reason for any discontinuation from the study will be documented in the subject's medical record and recorded on the appropriate eCRF.

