### **8.3.2 Independent Centralized Review of Efficacy Results**

Digital images from all tumor response assessments must be available to be sent to the independent central review (ICR) service at any time during the study. All images sent to the ICR service must be anonymized by the investigational sites and provided digitally as Digital Imaging and Communications in Medicine (DICOM) format. The investigator must assure that the images are of acceptable diagnostic quality and fulfill the requirements outlined in the Imaging Manual. Additional specific information on the handling (ie, collection, shipment, tracking) of the images sent to the ICR will be provided in the Imaging Manual.

The definitive treatment response assessment will be determined by the ICR service at the central imaging laboratory using the Lugano Classification ([Cheson, 2014](#)).

The reviewers at the central imaging laboratory will be board-certified radiologists, experienced and independent radiologists with strong expertise in clinical radiology as well as the use of Lugano Classification in clinical trials with novel hematology-oncology agents. The central reviewers must not be otherwise involved in this study, ie, listed or identified as investigator or sub-investigator who is directly involved in the treatment or evaluation of study subjects. Central reviewers will be isolated from knowledge of investigator PD assessments through read lock procedures and communication controls. Except for the baseline visit, the ICR will be blinded to the subject's identity and all other data (eg, demography, MT-3724 dose modification, TEAEs, disease characteristics).

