### 9.1 Statistical Hypothesis and Sample Size Determination

In Part 3, approximately 25 subjects will be enrolled as a continuation of the expansion of the MTD cohort with the intention to verify the safety, dose and dosing schedule (completion of the Phase 1b).

In Part 4, approximately 88 evaluable subjects will be enrolled. If at least 23 of 88 evaluable subjects respond at the end of Part 4, then the null hypothesis is rejected in favor of the alternative hypothesis and the effectiveness of MT-3724 as monotherapy will have been proven. Under the stated null and alternative hypotheses, Part 4 carries 90.4% power at the 1-sided alpha level of < 0.025.

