## **9.3.2    Efficacy Analysis**

The primary efficacy variable (Part 4) is the overall tumor response rate (ORR).

The secondary efficacy variables in Part 3 are overall response rate, DCR, DOR; and in Part 4 the secondary efficacy variables are the DCR, DOR, PFS, and OS.

The definitive treatment response assessment (ie, the tumor response used to derive the primary and secondary efficacy endpoints) will be determined by response assessment using the Lugano Classification ([Cheson, 2014](#)). The sponsor will have the definitive treatment response assessment determined by the blinded, ICR service at the central imaging laboratory using the Lugano Classification.

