### 9.3.2.2 Secondary Efficacy Variables

The secondary efficacy variables will be PFS, DCR, DOR and OS. All secondary efficacy variables will be determined from the radiological tumor scans according to the Lugano Classification for Lymphoma ([Cheson, 2014](#)) relative to the FAS population.

Secondary efficacy variables will be evaluated separately for Parts 3 and 4.

The DCR will be defined as the percent of subjects with objective response of CR, PR, or SD, (defined as SD for 6 months or longer). The DCR will be analyzed using similar methods as the ORR.

For subjects who continue to receive treatment after radiographic PD, and have confirmed PD at next assessment, the time of PD will be that of the first detection.

The DOR will be defined as the time from the first documented objective response (CR or PR) to the date of PD or death from any cause. Subjects who have not progressed at the time of data base lock will be censored at the date of their last tumor assessment.

The PFS will be defined as the time from the start of treatment with MT-3724 on C1D1 to the date of PD or death from any cause. Subjects who have not progressed at the time of data base lock will be censored at the date of their last tumor assessment.

For both DOR and PFS, those subjects who have no data on progression (eg, subjects who discontinued the study due to other reasons than progression and who were not followed up until progression) and/or have no data on tumor assessment after baseline and are still alive will be censored at the subject's date of first dose.

The OS will be defined as the time from the start of treatment with MT-3724 until death from any cause.

The DOR, PFS and OS will be summarized descriptively using the Kaplan-Meier methods (K-M median and corresponding 95% CI, quartiles, number of events, number censored, Kaplan-Meier figure). Since these methods assume missing data are missing at random, supportive analyses will be conducted assuming data are missing not at random.

As a secondary sensitivity analysis for efficacy (eg, study drug exposure, lines of prior therapy, DOR to prior therapy, subject subsets), the mFAS population will be utilized. The same statistical techniques will be applied on each efficacy endpoint on the mFAS population.

Data listings will be created to support each analysis and to present all efficacy data.

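### If DOR and PFS rest on the central review, progression called only by the investigator ends scanning and is then censored or dated late, which tends to lengthen both

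*Protocol*

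**What the plan says.** **Follow-up.** Table 1-1 schedules scans every 6 weeks until disease progression and does not say whose call counts. Protocol 8.3.1 has the site investigator make the preliminary read. After discontinuation for progression, 9.3.1 says: "Subjects who discontinue the study for disease progression will be followed only for OS". Subjects who leave for other reasons are followed for investigator-reported PFS and for OS. Under 8.1.5, subjects in CR, PR or SD have radiology until progression, death or new anticancer treatment.

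**Assessor.** Section 9.3.2 says that the definitive assessment feeds both primary and secondary endpoints, and: "The sponsor will have the definitive treatment response assessment determined by the blinded, ICR service at the central imaging laboratory". Section 8.3.2 adds: "Central reviewers will be isolated from knowledge of investigator PD assessments through read lock procedures and communication controls". The Synopsis (Efficacy Endpoints), however, gives the secondary efficacy endpoints to the investigator. The DOR row in 3.2 names no assessor.

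**Events and censoring.** Section 9.3.2.2 counts progression or death as the event for DOR and PFS, and continues: "Subjects who have not progressed at the time of data base lock will be censored at the date of their last tumor assessment". A further sentence there censors living subjects at first dose when there are no data on their progression. Its example is a subject who left for another reason and was not followed until progression. The section also promises supportive analyses under missing-not-at-random assumptions, without describing them.

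**Lack of benefit.** Section 7.1 allows withdrawal where "disease progression is not documented but the investigator determines that the subject requires alternative anticancer treatment".

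**The concern.** If the ICR decides progression, the site's call still ends scanning in practice. The ICR is shielded from that call, and no central confirmation before scans stop is described. A responder with investigator progression that the ICR does not read as progression then leaves the ICR-based risk set because someone saw failure. Kaplan-Meier treats that exit as independent of what would have followed.

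Three outcomes are possible for such a subject under 9.3.2.2:

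- alive at database lock: censored at the last tumor assessment;
- dies in OS follow-up: an event, but dated at death rather than at the earlier failure;
- read as having no data on progression: censored at first dose.

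The first two tend to lengthen DOR and PFS. The third fails for DOR, because first dose precedes the response from which DOR is measured.

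Withdrawal for lack of clinical benefit raises a related problem. Once new therapy starts, scanning ends, and the first-dose wording can be read as covering these subjects. No rule for new therapy is given.

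DOR is the only key secondary endpoint in Part 4. It tells the reader of a single-arm trial what the response rate is worth.

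**Working it through.** **1. The plan's own figure.** Section 9.1 sets the rule ("If at least 23 of 88 evaluable subjects respond at the end of Part 4") with one-sided alpha below 0.025 and power 90.4%. Exact binomial: P(X ≥ 23 | 88, 0.17) = 0.0201 and P(X ≥ 23 | 88, 0.32) = 0.9039. Both agree with the plan, and the ORR test is not affected by this point. The plan states no DOR or PFS figure, so there is none to reproduce.

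**2. Responders.** At the design rate, 88 × 0.32 = 28.2, about 28. A share d of 10%, 20% or 30% is about 3, 6 or 8 of them.

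**3. Assumptions (not in the documents).** Time to investigator progression is exponential with median 6 months before rounding up to the next scan. A share d of those progressions is not read as progression by the ICR at that scan. With continued scanning, the ICR would call progression one or two scans later, equally often. From the documents: scans every 6 weeks, which is 6/4.345 = 1.381 months.

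**4. Formulas.** Per-interval survival is s = 2^(−1.381/6) = 0.8525, so q = 1 − s = 0.1475. Eight scans fall within 12 months.

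- Censored at the discordant scan: S(12) = [1 − q(1 − d)]^8.
- Scans continued: S(12) = (1 − d)s^8 + d(s^7 + s^6)/2, with s^8 = 0.279, s^7 = 0.327 and s^6 = 0.384.

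The Kaplan-Meier median is the first scan at which survival is at or below 0.5.

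| d | S(12) censored | S(12) continued | Gap (points) | Median censored | Median continued |
|---|---|---|---|---|---|
| 10% | 0.320 | 0.287 | 3.3 | 6.9 mo | 6.9 mo |
| 20% | 0.366 | 0.294 | 7.2 | 8.3 mo | 6.9 mo |
| 30% | 0.418 | 0.302 | 11.6 | 9.7 mo | 6.9 mo |

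**5. Counting deaths.** A simulation keeps the same inputs but counts deaths within 18 months as events. Median survival after investigator progression is assumed to be 2 to 6 months. The 12-month gap falls to about 0.4–2 points at d = 10%, 1–5 at 20% and 1–7 at 30%.

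**6. If discordant calls carry no information.** Suppose the ICR hazard after a discordant call is the same as for anyone still in response. The 6-month estimate at d = 20% is then 0.605 censored against 0.601 with continued scanning. Across assumed medians of 3 to 9 months and d up to 40%, the 6-month gap is at most about 4 points.

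**The case against.** The strongest reply is that the premise is unsettled. If the Synopsis governs, investigator progression is simply an event and this censoring problem disappears. That stands: the point is conditional on the ICR reading in 9.3.2. Fixing the ICR as assessor would not remove it, however.

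Four further replies stand in part.

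- Deaths in OS follow-up are events, so censoring at the discordant scan is not the general outcome. This shrinks the bias (step 5) but does not reverse it, because death comes later than the failure.
- Some scans continue. Treatment beyond progression requires a repeat scan at 4 to 6 weeks. It applies only to radiological progression within 3 months of C1D1, at the investigator's option, so it does not reach responders who progress later.
- The missing-not-at-random analyses are promised, but nothing says that these exits become events. The supplied SAP cannot help: it rests on protocol v7.0 and covers Parts 1 and 2 and the extension study. A plan for Parts 3 and 4, and the Imaging Manual, may say more.
- DOR and PFS are descriptive, and no test depends on them.

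A reader might also infer that lack-of-benefit withdrawals can never become events. The documents do not support that. Such subjects are followed for PFS and OS, responders and stable subjects are scanned until new therapy, and death counts.

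**Conclusion.** The point holds conditionally. Under the ICR reading, the protocol takes a responder with investigator-only progression out of the risk set for an outcome-related reason, or dates the event late, and has no specific rule for it. The direction is upward for DOR (key secondary in Part 4) and PFS (an ordinary secondary endpoint), provided investigator progression predicts ICR progression. That the site's call is what stops scanning is an inference from the schedule and the ICR's isolation; it is not stated.

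The size cannot be fixed from the documents. On the assumptions above, the 12-month DOR rate rises by about 3, 7 and 12 points at d = 10%, 20% and 30% before deaths are counted, and by less after. The median does not move at d = 10%.

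A reader might multiply the median by 1/(1 − d) and infer +11%, +25% and +43%. That is a continuous-time approximation which ignores deaths. On the 6-week scan grid the figures are 0%, +20% (8.3/6.9) and +40% (9.7/6.9), also before deaths. Nor can a material bias be taken as established, since it is near zero if discordant calls carry no information. What is established is a gap in the rules that is cheap to close.

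**What to change.** 1. Reconcile the Synopsis, 9.3.1 and 9.3.2, and name one assessor for DOR and PFS in 9.3.2.2.
2. If it is the ICR, make one of the promised missing-not-at-random analyses a named supportive Kaplan-Meier analysis of DOR and PFS. The event is the earliest of ICR progression, investigator progression (or withdrawal for lack of clinical benefit) that ended scanning, and death.
3. Report it beside the ICR analysis, with the number of subjects who had investigator-only progression.
4. State that these subjects, and lack-of-benefit exits, are not censored at first dose.

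The rule should be written before database lock, so that it is not chosen with the results in view.

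The cost is a few lines of protocol and SAP text and one extra Kaplan-Meier table. Investigator assessments, reasons for discontinuation and deaths are already collected. The downside is that the supportive estimate mixes two assessors and will be less favourable than the ICR estimate, so it should be labelled as supportive.

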#### 9.3.1.1 Baseline Definition

The assessment obtained (and entered into EDC) at the most recent time before the start of MT-3724 treatment will be the baseline for all post-baseline assessments.

For all efficacy endpoints, the tumor scan obtained before MT-3724 Dose 1 during the screening (if available) will serve as the baseline; Pre-study tumor scan should be collected as close as possible to the start of treatment and evaluable for the ICR (ie, performed according to the Imaging Acquisition Guidance provided in the Imaging Manual).

### **9.3.1.2        Subject Disposition**

A detailed description of subject disposition will be provided. It will include:

- The number of subjects who were included in the FAS, safety and efficacy evaluable analysis sets
- A summary of subjects who complete the protocol
- A summary of reasons for subject discontinuation
- A summary of reasons for subjects with treatment failure
- An account of all identified protocol violations

All subjects enrolled in the study will be accounted for in the summation.

### **9.3.1.3        Demographic and Baseline Characteristics**

Demographic characteristics including age, gender, race, and ethnicity will be presented in the form of tabular summary statistics for all FAS subjects. Other subject baseline characteristics including weight, height, BMI, initial stage of disease, and performance status will be presented similarly.

## **9.3.2    Efficacy Analysis**

The primary efficacy variable (Part 4) is the overall tumor response rate (ORR).

The secondary efficacy variables in Part 3 are overall response rate, DCR, DOR; and in Part 4 the secondary efficacy variables are the DCR, DOR, PFS, and OS.

The definitive treatment response assessment (ie, the tumor response used to derive the primary and secondary efficacy endpoints) will be determined by response assessment using the Lugano Classification ([Cheson, 2014](#)). The sponsor will have the definitive treatment response assessment determined by the blinded, ICR service at the central imaging laboratory using the Lugano Classification.

### **9.3.2.1        Primary Efficacy Variable (for Part 4)**

The primary efficacy variable is the ORR. The ORR is defined as the percent of subjects with CR or PR determined by the blinded, ICR according to the Lugano Classification for Lymphoma ([Cheson, 2014](#)), relative to the FAS population.

Overall response rate will be summarized by number and percentage of subjects meeting the definition of ORR along with the corresponding 2-sided 95% binomial exact confidence intervals (CI), separately for Parts 3 and 4.

In Part 4, with  $n = 88$  subjects, if  $\geq 23$  ORRs are seen, the null hypothesis is rejected in favor of the alternative hypothesis and the effectiveness of MT-3724 as monotherapy will have been proven.

Subjects with missing disease assessments such that objective response cannot be determined will be assumed to be non-responders in the analysis.

### 9.3.2.2 Secondary Efficacy Variables

The secondary efficacy variables will be PFS, DCR, DOR and OS. All secondary efficacy variables will be determined from the radiological tumor scans according to the Lugano Classification for Lymphoma ([Cheson, 2014](#)) relative to the FAS population.

Secondary efficacy variables will be evaluated separately for Parts 3 and 4.

The DCR will be defined as the percent of subjects with objective response of CR, PR, or SD, (defined as SD for 6 months or longer). The DCR will be analyzed using similar methods as the ORR.

For subjects who continue to receive treatment after radiographic PD, and have confirmed PD at next assessment, the time of PD will be that of the first detection.

The DOR will be defined as the time from the first documented objective response (CR or PR) to the date of PD or death from any cause. Subjects who have not progressed at the time of data base lock will be censored at the date of their last tumor assessment.

The PFS will be defined as the time from the start of treatment with MT-3724 on C1D1 to the date of PD or death from any cause. Subjects who have not progressed at the time of data base lock will be censored at the date of their last tumor assessment.

For both DOR and PFS, those subjects who have no data on progression (eg, subjects who discontinued the study due to other reasons than progression and who were not followed up until progression) and/or have no data on tumor assessment after baseline and are still alive will be censored at the subject's date of first dose.

The OS will be defined as the time from the start of treatment with MT-3724 until death from any cause.

The DOR, PFS and OS will be summarized descriptively using the Kaplan-Meier methods (K-M median and corresponding 95% CI, quartiles, number of events, number censored, Kaplan-Meier figure). Since these methods assume missing data are missing at random, supportive analyses will be conducted assuming data are missing not at random.

As a secondary sensitivity analysis for efficacy (eg, study drug exposure, lines of prior therapy, DOR to prior therapy, subject subsets), the mFAS population will be utilized. The same statistical techniques will be applied on each efficacy endpoint on the mFAS population.

Data listings will be created to support each analysis and to present all efficacy data.

The value for the percent change from baseline in the sum of product of perpendicular diameters (SPD) as the measurement of tumor lesion size in each individual subject will be listed by time points. The values for the percent change from baseline in SPD values at each time point will be plotted for individual subjects (“spider plot”). The largest value for the percent change from baseline in SPD will be plotted on a histogram (‘waterfall’ plot).

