### Efficacy Endpoints

[figure not shown]
Tumor response and disease progression will be evaluated by the independent central review (ICR) for the Part 4 primary endpoint and the Part 3 secondary endpoint; and by the investigator for secondary efficacy endpoints (Parts 3 and 4) according to the Lugano Classification for Lymphoma ([Cheson, 2014](#)).

All subjects who receive at least 1 dose of study medication will be included in the full analysis set (FAS) for the efficacy analysis.

The efficacy analysis will include the ORR, DOR, and DCR at the Final Study Assessment Visit. Subjects who have not progressed at the time of analysis will be censored at the date of their last tumor assessment. Progression-free survival and OS will also be presented using Kaplan-Meier techniques.

The overall response rate (ORR) and DOR will be descriptively summarized; exact 95% confidence intervals (CI) will be produced.

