## 3.2 Part 4 Objectives and Endpoints

OBJECTIVES	ENDPOINTS
Primary	

 
To determine the efficacy of MT-3724 as monotherapy in subjects with relapsed or refractory DLBCL based on the ORR by the Lugano Classification for Lymphoma (Cheson, 2014)
 
	
 
overall response rate is defined as the proportion of subjects with either a CR or a PR as determined by independent, blinded central review
 

Key Secondary	

 
To determine additional measures of efficacy of MT-3724 as monotherapy in subjects with relapsed or refractory DLBCL
 
	
 
Duration of tumor response, defined as time from initial documentation of tumor response (complete response [CR] or partial response [PR]) to disease progression
 

Secondary	

 
To determine the safety of MT-3724 as monotherapy in subjects with relapsed or refractory DLBCL
 
	
 
adverse events
 
laboratory abnormalities
 
vital signs
 

 
To evaluate the effect of MT-3724 on the QT/QTc interval in subjects with relapsed or refractory DLBCL
 
	
 
electrocardiograms (ECGs)
 
adverse events suggestive of cardiotoxicity
 

 
To determine additional measures of efficacy of MT-3724 as monotherapy in subjects with relapsed or refractory DLBCL
 
	
 
overall response rate, defined as the proportion of subjects with either a CR or a PR as determined by investigator assessment
 
disease control rate (DCR), defined as proportion of subjects who have achieved CR, PR and SD (defined as SD for 6 months or longer)
 
progression-free survival (PFS), defined as the time from study enrollment to the earliest date of disease progression or death from any cause
 
overall survival (OS), defined as the time from study enrollment to death from any cause
 

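### Duration of response, the Part 4 key secondary endpoint, has two event definitions and two assessors, and its censoring rules contradict its own definition

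*Protocol*

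**What the plan says.** **DOR event.** Protocol Section 3.2 lists as the only key secondary endpoint of Part 4: "Duration of tumor response, defined as time from initial documentation of tumor response (complete response [CR] or partial response [PR]) to disease progression". The synopsis tables for Parts 3 and 4 and Section 3.1 also stop at progression. Section 9.3.2.2 instead counts either event, measuring from the earliest documented response: "CR or PR) to the date of PD or death from any cause".

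**Assessor.** The synopsis (Efficacy Endpoints) limits ICR to the primary endpoint of Part 4 and one secondary endpoint of Part 3. The same sentence goes on: "and by the investigator for secondary efficacy endpoints (Parts 3 and 4) according to the Lugano Classification for Lymphoma". Section 9.3.2 describes the definitive response assessment as "ie, the tumor response used to derive the primary and secondary efficacy endpoints" and has the blinded ICR service determine it. Section 9.3.2.2 names no assessor. The synopsis and Section 9.3.1 describe progression-free survival (PFS) in long-term follow-up as investigator-reported.

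**Censoring.** For both DOR and PFS, Section 9.3.2.2 censors subjects without progression at database lock at their last tumor assessment. The synopsis has a similar sentence. Neither excepts subjects who died. A further rule in Section 9.3.2.2, also for both endpoints, censors certain living subjects at the date of first dose. Its example is a subject who left for reasons other than progression and was not followed until progression.

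**Lesser items.** Section 3.2 has PFS "defined as the time from study enrollment to the earliest date of disease progression or death from any cause", and starts overall survival (OS) at enrollment too. Section 9.3.2.2 says "The PFS will be defined as the time from the start of treatment with MT-3724 on C1D1", and starts OS at first treatment as well. The synopsis states: "The efficacy analysis will include the ORR, DOR, and DCR at the Final Study Assessment Visit". The Schedule of Activities has no visit of that name.

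**The concern.** Part 4 is single-arm and open-label, so the response rate and the duration of those responses will be read together. The response rate is centrally reviewed. If DOR follows the synopsis, it may describe a different set of responders, with progression dated by a different reader. If DOR follows the objectives tables, or the literal censoring sentence in Section 9.3.2.2, a responder who dies without documented progression is removed at the last scan instead of counted as an event, and the reported duration is longer. The protocol gives no order of precedence between its sections. The supplied SAP rests on protocol v7.0 and covers Parts 1 and 2; its own DOR (SAP Section 1.3.5.2) ends at recurrence or progression without naming death. In an open-label study, leaving this choice open until data have been seen is avoidable discretion over a key endpoint.

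**Working it through.** **1. The plan's own figure.** Section 4.1.2 gives a null rate of 17%, an alternative of 32%, n = 88, rejection at 23 or more responders, and 90.4% power at one-sided alpha below 0.025. Exact binomial:

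- P(X ≥ 23 | 88, 0.17) = 0.0201
- P(X ≥ 23 | 88, 0.32) = 0.9039

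Both agree with the protocol. DOR, PFS and OS do not enter this rule. No power or threshold is stated for them.

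**2. What each text does with a responder who dies without documented progression.**

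| Text | Treatment of the death |
|---|---|
| Objectives tables (synopsis, 3.1, 3.2) | Not an event |
| 9.3.2.2, DOR definition | Event |
| 9.3.2.2 and synopsis, censoring sentences read literally | Censored at last tumor assessment |

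The first-dose rule in 9.3.2.2 is limited to subjects still alive. The last-assessment rule carries no such limit.

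**3. The first-dose rule applied to DOR.** DOR starts at response, which is after first dose, so a censoring date at first dose gives a negative duration. A responder who stops for another reason and is not followed to progression fits the rule's example. The same subject also falls under the last-assessment rule, so two censoring dates apply.

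**4. Size of the event conflict.** Let h be the total hazard of progression or death after response, and f the share of first events that are deaths without progression. With exponential times:

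- median, progression or death = ln 2 / h
- median with deaths censored = ln 2 / [h(1 − f)]
- ratio = 1 / (1 − f)

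| Assumed f | Ratio | If the deaths-censored median is 6 months, the progression-or-death median is |
|---|---|---|
| 10% | 1.11 | 6 × 0.9 = 5.4 months |
| 20% | 1.25 | 6 × 0.8 = 4.8 months |
| 30% | 1.43 | 6 × 0.7 = 4.2 months |

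Both f and the 6-month median are assumptions. The formula censors at the date of death; censoring at the last scan is not modelled.

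**5. Size of the assessor conflict.** The documents give no discordance rate between ICR and investigator. At the decision threshold there are 23 responders; at the alternative, 0.32 × 88 ≈ 28. One subject reclassified is 1/23 = 4.3% to 1/28 = 3.6% of the DOR set. That is only the weight of one subject, not an estimate of how many would change.

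**6. Time origin.** Enrollment has no date definition. A Schedule of Activities footnote counts the 35-day screening window back from enrollment; Section 8.1.1 counts it back from Cycle 1 Day 1 (C1D1). The two dates may therefore nearly coincide. For an assumed gap of 0 to 35 days the shift is 0 to 35/30.4375 = 1.15 months; a 7-day gap is 0.23 months. Against the 6.3-month OS of the retrospective study cited in Section 2.1.3, 7 days is 3.7% and the 35-day bound is 18.3%.

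**The case against.** Section 9.3.2.2 says DOR, PFS and OS are summarized descriptively. DOR is called key secondary but has no hypothesis, alpha or threshold, and the only decision rule is ICR response in at least 23 of 88. Section 9 also assigns the detailed methods for Parts 3 and 4 to a SAP that is not among the documents. All this stands and limits the severity. It does not remove the contradiction: Section 9 requires major departures from the protocol to appear in an amendment as well.

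On the assessor, Sections 8.3.2 and 9.3.2 both call the ICR reading definitive, and Section 3.2 attaches investigator assessment only to the secondary response rate. The main contrary text is one synopsis sentence, supported by the investigator-reported follow-up PFS. ICR is thus the better-supported reading, but the synopsis sentence is plural and unrestricted, so the conflict remains.

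On censoring, a sensible analyst would let the stated event definition override the loose sentence. That is probably the intent, but the text does not say it.

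Two stronger readings are tempting. A reader might infer from the Final Study Assessment Visit that a responder who later progressed is scored as a non-responder. Section 9.3.2.1 defines the response rate without any time-point restriction. The synopsis phrase also covers DOR, which could not be measured if progressed responders dropped out. It is a terminology error, not a second definition of response. A reader might also infer that ICR already holds every image needed. Section 8.3.2 says only that images must be available to send; Section 8.1.5 lets follow-up radiology come from medical records, and Section 9.3.1 has follow-up PFS reported by investigators.

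**Conclusion.** The point holds, at should-fix level. The current protocol gives DOR two event definitions and two assessors, and Section 9.3.2.2 contains censoring rules that conflict with its own definition. The direction is known: censoring deaths lengthens DOR. The size is conditional: 11% to 43% on the median if 10% to 30% of events are deaths without progression and times are exponential. The documents supply no value for that share, and none for reader discordance.

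The conflict does not touch the primary test, whose alpha and power are as stated. The PFS and OS origin conflict is real but probably small, with 35 days as an assumed upper bound. Together with the undefined visit name, it calls for minor clarification only.

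**What to change.** 1. State one DOR definition identically in the synopsis (objectives tables for both parts and Efficacy Endpoints) and in Sections 3.1, 3.2, 9.3.2 and 9.3.2.2: first ICR-assessed CR or PR to ICR-assessed progression or death from any cause, in ICR responders. Keep the investigator version as a sensitivity analysis.
2. Rewrite the censoring sentences in the synopsis and Section 9.3.2.2 so that only subjects alive without progression are censored, at the last tumor assessment, and for DOR never before the response date. Changing the definition alone would leave the handling of deaths unsettled.
3. Name one main assessor for disease control rate and PFS, with the other as sensitivity.
4. As minor clarifications, use C1D1 as the single origin for PFS and OS, and delete or replace the undefined visit name.
5. Carry the same wording into a SAP for Parts 3 and 4.

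The cost is mainly an amendment of wording, best made before Part 4 data accrue. If ICR is the main assessor for PFS, there is a small added cost in collecting follow-up images. The same applies to DOR for responders who stop treatment without progression, because Sections 8.1.5 and 9.3.1 currently allow medical-record and investigator-reported follow-up.
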